10.2 Identity of Clinical Trial Material

Ta1 clinical trial material (CTM) will be generously provided for this study by SciClone, Inc (China). Ta1 is contained, stored, and dispensed from individual tamper-proof glass vials with 1.6 mg Ta1 as a lyophilized cake containing 5% mannitol, buffered with phosphate to pH 6.4 - 7.3. Vials are reconstituted with 1 mL of supplied diluent (sterile Water for Injection), prior to subcutaneous (SC) administration.

10.3 Labeling and Packaging

ZADAXIN lyophilisate for solution for injection is a sterile, white to off-white lyophilized powder, containing Ta1 manufactured by solid-phase peptide synthesis.

The CTM intended for investigational use will be stored in a locked area with limited access, refrigerated between 2°C and 8°C.

10.4 Study Drug Accountability

The Investigator or designed site personnel are responsible for ensuring adequate accountability of all used and unused CTM. This includes acknowledgement of receipt of each shipment of CTM (quantity and condition), and documentation of dispensing, returns, and destruction of CTM. Dispensing records will document quantities of CTM received. Quantities dispensed will be documented, including date dispensed, subject identification number, and the initials of the person dispensing the CTM. Study drug accountability records must be readily available for inspection by regulatory authorities at any time.

The Investigator will not allow CTM to be given to any subject not enrolled into the treatment arm of the study or any unauthorized person.

10.5 Method of Assigning Subjects to Treatment

Subjects who meet all inclusion and exclusion criteria will be centrally randomized 1:1 to receive either no treatment or 1.6 mg Ta1 in 1 mL doses to be delivered twice weekly after dialysis (with treatment days separated by at least 2 full days without Ta1 injection), via SC injection for 8 weeks, in accordance with a computer-generated randomization schedule prepared by the Inova Biostatistical core.

Randomization will be stratified by dialysis site.

10.6 Selection of Doses

For those randomized to the treatment arm, Ta1 will be administered SC at doses of 1.6 mg twice weekly after dialysis for 8 weeks, similar to the dose and regimen used in many previous clinical trials and in commercial use in China.

This dose is supported by safety studies which show that Ta1 is well tolerated; in particular, no safety signals were seen in studies which enrolled subjects with: acute respiratory disease due to cytomegalovirus (CMV) or pneumonia, chronic obstructive pulmonary disease, severe lung infections, ESRD requiring hemodialysis, chronic infections (hepatitis B, hepatitis C, HIV/AIDS), cancer and those being treated with chemotherapy, or elderly subjects.

Pharmacokinetic studies show that there is no accumulation of Ta1 and the $T_{1/2}$ is 2 hours.

The proposal to evaluate a single dose rather than dose escalation is based on previous studies which have shown that doses above 1.6 mg showed little, if any, improvement in response, and the mechanism of action of Ta1 (immune modulation rather than directly targeted therapy) suggests that the optimal dose should be equivalent no matter which indication is being investigated.

Support for the safety of the proposed dosing regimen is also seen in the nonclinical safety studies, which showed no adverse effects in rodents (mice and rats) at doses up to 20 mg/kg/day for acute dosing or 6 mg/kg/day for 6 months with repeat dosing; and no adverse effects were seen in marmosets dosed at 1 mg/kg/day for 6 months of repeat dosing. Conservatively, the marmoset no adverse effect level (NOEL) of 1 mg/kg/day represents a 50-fold safety margin over dosing of 1.6 mg.

10.7 Concomitant Therapy

Any concomitant therapy used from the time a subject signs an ICF through the 6-month end of study visit will be recorded on the CRF. In addition, for any serious adverse events (SAEs) that require medication for treatment, those medications will be recorded on the concomitant medications page. The medication name, dose, route of administration, start and stop dates and indication for use will be recorded.

There are no prohibited medications for this study protocol.

10.8 Standard of Care

The Investigator will follow routine standard of care for elderly renal dialysis patients.

The Investigator or any physician member of the Nephrology Associates of Northern Virginia may prescribe any concomitant medication or supportive therapy deemed necessary to provide adequate standard of care.

Subjects who have been determined to have received investigational products (exclusion criteria #6) either 30 days prior to their initiation of the study, or during the course of the study, will not be removed from the study; however, this fact will be recorded.

11 ASSESSMENTS

11.1 Efficacy Assessments

Clinical and laboratory evaluations of each participating subject will occur at two-week intervals. This will include initial medical history and physical examination (Investigator), a brief interview, symptom inventory and examination (vital sign, physical exam; see Appendix 1 for symptom questionnaire) twice weekly during the study period (research nurse), and serial laboratory evaluations obtained every 2 weeks during the treatment phase and then monthly for a total of 6 months.

All clinical and laboratory data will be entered on the subject's CRF with data entered at times indicated in Table 1 and secured in a cloud-based secure archive. The clinical data will include a symptom inventory, change in medical status (infection or non-infection), hospitalizations, intensive care unit admission, requirement for mechanical ventilation (respirator or extracorporeal membrane oxygenation [ECMO]), length of stay in the hospital and in the ICU, and survival. If subjects report respiratory symptoms (see Appendix 1 for symptom questionnaire), they will be tested for SARS-CoV2 and influenza. If these tests are negative, a full respiratory viral infection panel will be run.

Clinical Study Protocol: Ta1 to Prevent COVID-19 Infection in Elderly Renal Dialysis Patients

In addition to screening for SARS-CoV2, routine complete blood count (CBC), and standard chemistry evaluations, additional markers of infection including procalcitonin, C-reactive protein (CRP), and lactate dehydrogenase (LDH) will be followed. Further, T lymphocyte subsets CD4 and CD8 will be determined by flow cytometry at enrollment, at eight weeks and upon completion of the six-month project.

Aliquots of serum will be cryopreserved for all subjects to assess COVID-19 antibody throughout the course of this study once the methodologies have been worked out and the assays are commercially available. It is anticipated that these serum samples will all be run upon completion of the trial.

Subjects who report respiratory illness symptoms (see Appendix 1 for symptom questionnaire) at the designated inventory times (Table 1) or in the interval between those designated times will be tested for COVID-19 virus. If the COVID-19 assay is positive, this will complete the treatment phase of the research protocol for that individual. However, the subject will remain on study with continuation of the designated assessments to assess severity of disease (e.g., need for hospitalization, ICU management, mechanical ventilation, mortality).

In addition to infection with COVID-19, the following assessments will be collected and recorded at intervals in Table 1:

- Need for hospitalization
- Hospital length of stay
- ICU admission
- ICU length of stay
- Mechanical ventilation
- Mortality
- Incidence of secondary infections
- CD4, CD8, CD4/CD8.

Assessment for secondary infections will be documented in the CRF. Sites will be required to record all infections occurring from the time of enrollment until completion of the study 6 months after enrollment. Data will include the site of the infection, the evidence of infection, the organism cultured, and the antimicrobial susceptibility data.

The study will use the Inova Central Laboratory for conducting all laboratory investigations included in this study.

11.2 Safety Assessments

Safety will be assessed by collecting, recording AEs and reviewing all adverse events in a timely fashion. The investigators, study nurse and clinical trials specialist will meet weekly (Safety Meeting) for this purpose, or as needed if a serious adverse event is recognized that requires immediate attention.

Each enrolled subject will be briefly examined at two week intervals. Included in that exam will be vital signs, examination of the head, eyes, ears nose and throat and auscultation of the chest.

Routine clinical labs which include complete blood count with white blood cell differential and comprehensive metabolic panel (sodium, potassium, chloride, carbon dioxide, glucose, blood urea nitrogen, creatinine calcium, total protein, albumin, total protein, aspartate amino transaminase, alanine amino transaminase) will be reviewed for each research subject at two week intervals. These data will be reviewed at the weekly Safety Meeting.

The Investigator will assess all abnormal clinical laboratory results for clinical significance in a timely fashion. A notation of clinically significant or not clinically significant, with initials and date, will be documented on the respective laboratory report next to any abnormal value. An abnormal laboratory value of clinical significance will be considered and documented as an AE if, in the opinion of the Investigator, it is clinically significant and not considered part of the underlying clinical condition.

Investigators will classify adverse events and laboratory findings as mild, moderate, or severe based on the perceived clinical significance of the event and laboratory finding in the patient. The Investigator will follow proper AE and SAE reporting procedures.

12 STUDY PROCEDURES

12.1 Schedule of Events

A schedule of study procedures is outlined in Table 1.

12.2 Screening

Once FDA and IRB approval are obtained, the research team will promptly initiate the process of subject recruitment. Recruitment of all subjects will be completed in four months and the observation phase in one year. Posters and leaflets will be prepared for distribution at the study sites. Interested individuals will be directed by site personnel to discuss the study with any of our research staff and informed consent will be obtained by the Investigator or research nurse.

The following screening observations and procedures will be completed prior to randomization:

- Obtain a signed Health Insurance Portability and Accountability Act (HIPAA) authorization
- Assess a subject against the inclusion/exclusion criteria
- Obtain a signed IRB-approved informed consent (ICF)
- Perform physical exam and obtain medical history
- Assess performance status (Karnofsky Performance Scale)
- Take a nasopharyngeal swab to test for SARS-CoV2
- Draw blood sample for:
 - Complete blood count (CBC) and standard chemistry surveys
 - Nonspecific markers of infection (procalcitonin, CRP, and LDH)
 - CD4, CD8 (flow cytometry)
 - Serum cryopreservation for future serologic assay once it is available.

12.3 Weekly Study Procedures (for 8 weeks)

The following observations and procedures will be conducted:

Clinical Study Protocol: Ta1 to Prevent COVID-19 Infection in Elderly Renal Dialysis Patients

- Record abbreviated physical exam, height, weight, vital signs
- Record respiratory virus symptoms (see Appendix 1 for questionnaire)
- Record comorbidity signs and symptoms
- Record any concomitant medications
- Record AEs and SAEs
- Record secondary infections
- Administer dose of Ta1 (or no treatment) after dialysis (twice per week, with at least two full days between treatments).

12.4 Every Other Week Study Procedures (for 8 weeks)

The following observations and procedures will be conducted:

- Record any concomitant medications
- Record AEs and SAEs
- Record secondary infections
- Draw blood sample for serology
 - Routine complete blood count (CBC) and standard chemistry surveys
 - Serum cryopreservation for future serologic assay once it is available.

12.5 Additional Blood Draws at Week 4, Week 8

- Draw blood sample for serology
 - Nonspecific markers of infection (procalcitonin, CRP, LDH)
 - CD4, CD8 (flow cytometry).

12.6 Additional Procedures if respiratory infection symptoms are seen

- Take nasopharyngeal swabs for analysis
 - SARS-CoV2 and influenza assay
 - If SARS-CoV2 and influenza assay are negative: full respiratory virus panel.

12.7 Monthly Follow-up Visits (for 4 months)

The following observations and procedures will be conducted:

- Record vital signs, including temperature, systolic and diastolic blood pressures, heart rate, and respiration rate
- Record respiratory virus symptoms (see Appendix 1 for questionnaire)
- Record any concomitant medications
- Record AEs and SAEs
- Record secondary infections
- Draw blood sample for serology
 - Routine complete blood count (CBC) and standard chemistry surveys
 - CD4, CD8 (flow cytometry)
 - Serum cryopreservation for future serologic assay once it is available.

13 ADVERSE EVENT REPORTING

Throughout the study, AEs will be recorded onto the CRF regardless of whether or not the AEs are considered study treatment-related. All AEs with onset dates after the date the subject signed the ICF through the second week 8 visit will be recorded as an AE on the CRF. Conditions existing prior to signing the ICF will be recorded as part of the subject's medical history. All SAEs with onset dates after the subject signs the ICF through the second week 8 visit must be recorded following the guidelines in Sections 13.4 and 13.8. To avoid confusion, AEs will be recorded in standard medical terminology.

The Investigator is responsible for assessing the relationship of AEs to CTM (see Section 13.3).

13.1 Adverse Event Definition

An *adverse event* is any untoward medical occurrence in a subject administered an investigational product and which does not necessarily have a causal relationship with this treatment. An AE can be any unfavorable and unintended sign (for example, an abnormal laboratory finding), symptom or disease temporally associated with the use of an investigational product, whether or not considered related to this investigational product. This includes an event that emerges during treatment having been absent pre-treatment or an event that worsens relative to the pretreatment state. Recurrent symptoms of a chronic preexisting condition are not considered AEs, unless they occur in a worse or unexpected pattern during CTM administration.

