4 ABBREVIATIONS

Abbreviation	Full Term
ADL	activities of daily living
AE	adverse event
ARDS	acute respiratory disease
CBC	complete blood count
CFR	Code of Federal Regulations
CMV	cytomegalovirus
COPD	chronic obstructive pulmonary disorder
CRF	case report form
CRP	C-reactive protein
CTM	clinical trial material (i.e., ZADAXIN or placebo)
ESRD	end-stage renal disease
FDA	Food and Drug Administration
GCP	good clinical practice
HIPAA	Health Insurance Portability and Accountability Act
HIV	human immunodeficiency virus
ICF	informed consent form
ICH	International Conference on Harmonisation
ICU	intensive care unit
IL	interleukin
IND	investigational new drug
IRB	Institutional Review Board
LDH	lactate dehydrogenase
mL	milliliter
mg	milligram
2019-nCoV	2019 novel coronavirus
NK	natural killer
NOEL	no observable effect level
SAE	serious adverse event
SARS	severe acute respiratory syndrome
SC	subcutaneous(ly)
Ta1	ZADAXIN thymalfasin, thymosin alpha 1
Th1	Th1-type T cell
TLR	Toll-like receptor
WHO	World Health Organization

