13.4 Recording of Adverse Events

All AEs with onset dates after the subject signed the ICF through the 6-month visit will be recorded on the CRF. All AEs must be recorded on the appropriate CRF, regardless of their severity or relationship to the CTM. All AEs that meet the seriousness criteria (Section 13.6) will be recorded as an SAE.

All clinical events are to be recorded, including both observed (such as any reaction at injection sites) and volunteered problems, complaints, or symptoms. The need to capture this information does not depend upon the clinical event's association with the use of the CTM. Adverse events resulting from concurrent illnesses, reactions to concurrent medications, or clinically significant progression of disease states are also to be recorded.

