13.6 Serious Adverse Event Definition

A *serious adverse event* (SAE) is defined as any AE occurring at any dose regardless of relationship to CTM that results in any of the following outcomes:

- Death
- Is life-threatening
- Requires inpatient hospitalization or prolongation of existing hospitalization
- Results in persistent or significant disability or incapacity
- Other significant medical events.

In addition, all AEs assessed by the investigator with severity of Grade 4 or Grade 5 should be reported as SAEs. An important medical event that may not result in death, be life-threatening or require hospitalization may be considered an SAE when, based upon appropriate medical judgment, it may jeopardize the subject and may require medical or surgical intervention to prevent one of the outcomes listed above.

Complications that occur during hospitalization are AEs. If a complication prolongs a hospitalization, it is an SAE.

As used in this study, the term *inpatient hospitalization* is defined as formal admission to a hospital for medical reasons or evaluation in the Emergency Department of a hospital even if not admitted.

When an SAE occurs in a subject receiving a product as a concomitant medication, the SAE must be processed and reported.

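### The AE and SAE definitions are tied to receipt of study drug, so they do not fit the untreated control arm and conflict with the rules that record AEs in every patient

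*Combined protocol and SAP*

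**What the plan says.** Section 13.1 defines an AE as "any untoward medical occurrence in a subject administered an investigational product". Its later sentences keep the same anchor. An AE may be a "symptom or disease temporally associated with the use of an investigational product", and the definition includes "an event that worsens relative to the pretreatment state". Recurrent symptoms of a chronic condition that was already present are left out "unless they occur in a worse or unexpected pattern during CTM administration".

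Section 13.6 defines an SAE as "any AE occurring at any dose regardless of relationship to CTM" that leads to one of the listed outcomes, so it inherits whatever 13.1 includes or omits.

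Section 10.5 has patients "centrally randomized 1:1 to receive either no treatment or 1.6 mg Ta1", and Section 10.1 confirms that controls get no injections. The abbreviation list nevertheless expands CTM as "clinical trial material (i.e., ZADAXIN or placebo", although the trial has no placebo.

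The recording rules are broader. Section 13.4 asks for every clinical event, whatever its link to CTM, and adds that "clinically significant progression of disease states are also to be recorded". Sections 13.4, 13.5 and 13.7 start AE and SAE collection at consent and run it to the 6-month visit. Sections 12.3, 12.4 and 12.7 and Table 1 list AE and SAE recording without separating the arms.

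**The concern.** The wording of 13.1 and 13.6 would serve a placebo-controlled trial, where both arms are given something. Here one arm is given nothing, and no sentence in 13.1 says how an event in an untreated patient is to be classified. The recording rules in Sections 12 and 13.4 use the term AE, and 13.1 is where that term is defined, so site staff must decide which text governs.

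There is no placebo, so staff know each patient's arm when they make that decision. Patients are 60 or older, on dialysis, and by the protocol's own account often have other illnesses. Many events will come from underlying disease, and the concurrent control rate is the main means of separating those from drug effects. If the definition leads staff to record fewer background events in controls, Ta1 will appear to cause AEs that it does not cause. AEs are one of the three safety endpoints in Section 8.3, and the DSMB in Section 13.9 is asked to judge the balance of risk and benefit.

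**Working it through.** The documents give no AE rate and no power for safety, so there is no stated figure to reproduce. The check is of the text, followed by an illustration.

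**Step 1. Does each provision reach an untreated control?**

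| Place | Condition | Reaches controls? |
|---|---|---|
| 13.1, core definition | Patient was given an investigational product | No, read literally |
| 13.1, recurrent chronic symptoms | Worse or unexpected while CTM is given | No; on Ta1, only during the 8 treatment weeks |
| 13.6, SAE | An AE as in 13.1, with reference to dose | No, read literally |
| Section 7 | Controls follow the same protocol without Ta1 | Yes |
| 12.3, weekly list | Includes AE recording; its dosing item names both Ta1 and no treatment | Yes |
| 12.4, 12.7, Table 1 | AE recording, no split by arm | Yes |
| 13.4, 13.5, 13.7 | Recording starts at consent, before any product | Yes |

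The start at consent matters: a rule that collects AEs before anyone is dosed cannot make dosing a condition for an AE. The two groups of provisions cannot both be followed as written.

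**Step 2. How far does the CTM-administration limit go?** It applies to recurrent symptoms of a chronic pre-existing condition. The sentence before it counts any event that is worse than the pretreatment state and carries no such limit. The limit also removes recurrent symptoms in Ta1 patients after week 8, so for those symptoms the arms differ only during weeks 1 to 8.

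**Step 3. Illustration of differential capture.** Inputs:

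- Patients per arm: 240/2 = 120 enrolled, or (240 − 40)/2 = 100 with complete data (Section 15.1, 1:1 allocation).
- True AE risk p, equal in both arms: assumed 40%, range 20% to 60%.
- Share c of control patients with an AE who are recorded as having one: assumed. Capture on Ta1 is taken as complete.

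Recorded control risk is q = c × p, so the false excess on Ta1 is d = p − q = p(1 − c). The chance that it looks nominally significant against Ta1 (two-sided 0.05) is Φ[(d − 1.96·se0)/se1], with se0 = √(2·m(1 − m)/n), m = (p + q)/2, and se1 = √((p(1 − p) + q(1 − q))/n).

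Example with p = 0.40, c = 0.75, n = 100: q = 0.30, d = 0.10, m = 0.35, se0 = √(2 × 0.35 × 0.65/100) = 0.0675, se1 = √((0.24 + 0.21)/100) = 0.0671. Then (0.10 − 1.96 × 0.0675)/0.0671 = −0.48, and Φ(−0.48) = 0.32.

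| Control capture | Recorded control risk | False excess | Chance, 100 per arm | Chance, 120 per arm |
|---|---|---|---|---|
| 100% | 40% | 0 points | 2.5% | 2.5% |
| 90% | 36% | 4 points | 8% | 9% |
| 75% | 30% | 10 points | 32% | 37% |
| 50% | 20% | 20 points | 88% | 93% |

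At 75% capture and 100 per arm, risks of 20% to 60% give a false excess of 5 to 15 points and a chance of 15% to 57%. Section 15 plans no between-arm AE test; the chances only show how convincing a spurious excess could look.

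**The case against.** The strongest reply is that the operational text makes the intention clear. Controls follow the same protocol, the weekly list names untreated patients, Table 1 does not separate the arms, and 13.4 asks for all clinical events. A trained site would probably record control AEs, and then there is no bias at all. This stands as far as intention goes. It does not settle the classification, because most of these provisions use the term that 13.1 defines, and 13.4 does not say whether a control's clinical event counts as an AE for the safety endpoint.

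Three stronger readings are tempting, and the documents support none of them:

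- **A reader might infer that controls have no AEs by definition**, and so expect, at an assumed 20% event rate, 0.20 × 120 = 24 Ta1 patients against 0 controls. That follows only if 13.1 and 13.6 are read alone and the recording rules are ignored.
- **A reader might infer that any worsening of existing disease counts only while Ta1 is being given.** The limit is narrower than that (Step 2), and 13.4 also asks for clinically significant disease progression.
- **A reader might infer that the DSMB has no valid comparator.** Section 8.2 collects hospitalisation, ICU admission, comorbidity changes, other infections and deaths, with no split by arm. Vital signs and laboratory values do not depend on 13.1, and the stopping basis in 13.9 is treatment-related AEs.

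These other data compensate only in part. Section 13.6 counts an Emergency Department evaluation without admission as hospitalisation, whereas the efficacy endpoint in 8.2 needs a referral for admission. Section 11.2 turns clinically significant laboratory findings into AEs, which brings the 13.1 wording back in. Judging whether an AE is treatment-related is also harder without a sound background rate.

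**Conclusion.** The concern holds as a contradiction between definition and recording rules. Sections 13.1 and 13.6, read literally, do not cover the half of the patients who receive no product. Sections 7, 12, 13.4, 13.5 and 13.7 and Table 1 do cover them. With arm known to staff, this invites under-recording of background events in controls.

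If that happens, the direction is against Ta1. The size depends on how far 13.1 rather than 13.4 governs practice, which the documents cannot show. The figures of 4 points at 90% capture and 10 points at 75% rest on an assumed 40% true risk in both arms and complete capture on Ta1; with full control capture the false excess is zero. It is a risk to the safety comparison, not a demonstrated bias, and it does not touch the primary efficacy endpoint. It should be corrected because the correction is easy and the control AE rate is needed to interpret the AEs on Ta1.

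**What to change.** - In 13.1, define an AE as any untoward medical occurrence in an enrolled patient in either arm, whether or not CTM was received.
- In 13.1, replace the references to CTM administration, to treatment and to the pretreatment state with ones that apply to both arms, for example change from baseline during the study recording period.
- In 13.6, add the control arm after the reference to dose.
- Reconcile 13.1 with 13.4 and Section 12, stating that events recorded in controls count as AEs in the safety endpoint.
- When the recording period is named, settle its end: the opening of Section 13 stops at the second week 8 visit, while 13.4, 13.5 and 13.7 run to 6 months. This is a separate inconsistency, but the new wording will depend on it.

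The cost is a few phrases in Section 13 and a few more control events to record and code. No visits are added, because AE recording is already scheduled for every patient.
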